9.6 Intraocular Pressure

IOP and change from baseline in IOP will be summarized by analysis visit for the analysis eye and the fellow eye, separately. Subjects with any increase of ≥ 10 mmHg in IOP at any follow-up visit will be listed.

10 CHANGES FROM THE PROTOCOL

10.1 FVA Parameters to be Analyzed

The variable "FVA" was removed from the list of FVA parameters to be analyzed in Section 2.2.2.1 and Section 8.2.1 due to this variable was not in the FVA system outputs and not collected on the eCRF.

10.2 Scale Conversion of the FVA Parameters

FVA parameters (LogMAR FVA, starting VA, minimum VA, and maximum VA) were supposed to be collected on LogMAR scale on the eCRFs. However, due to the first time use of the FVA system by Santen and sites, and given the FVA system User Manual as well as the system outputs were all written in Japanese, there was some confusions regarding which numbers to be read off from the FVA system output. Instead of the LogMAR scores, the decimal VA scores were instructed to be recorded on the eCRFs. Therefore, at the data analysis stage, the following formula will be used to convert decimal VAs to LogMAR VAs before any data analyses are performed:

 $LogMAR VA = - log_{10}(decimal VA)$

10.3 Sensitivity Analysis of the Primary Efficacy Endpoints

The protocol stated "Changes from baseline in VMR and variance of OSI will also be summarized by categorical change in CFS (-5, -4.5, -4, -3.5, -3, -2.5, -2, -1.5, -1, 0, +1 unit change) and by analysis visit (Month 1, Month 2, and Month 3)." (Section 12.3 of the protocol). This is now changed to "Changes from baseline in VMR and variance of OSI will also be summarized by categorical change in CFS (-5, -4.5, -4, -3.5, -3, -2.5, -2, -1, 0, +1 and +2-unit change) and by analysis visit (Month 1, Month 2, and Month 3)." in Section 8.1.2 of this SAP to fix some typographical errors in the categories.

10.4 Correlation Analysis for Data Collected from the Same Visit

Correlation analyses were added to Section 8.2.3.1 for correlation between the change from baseline in CFS vs. change from baseline in TBUT, Schirmer's test, HOA RMS, VAS symptom scores (photophobia and blurred vision, separately), and visual acuity (BCDVA and UDVA, separately). Also added were correlation between the change from baseline in logMAR FVA vs. change from baseline in OSI parameter (OSI and variance of OSI, separately), TBUT, Schirmer's test, HOA RMS, VAS symptom scores (photophobia and blurred vision, separately), and visual acuity (BCDVA and UDVA, separately), and visual acuity (BCDVA and UDVA, separately).

10.5 Correlation Analysis of the Lagged Data – Change from Baseline in CFS vs. Change from Baseline in VAS Symptom Scores

Two lagged analyses were added to Section 8.2.3.2 to check the correlation between the change from baseline in CFS vs. the lagged change in VAS symptom scores (photophobia and blurred vision, separately).

12 APPENDICES

12.1 Appendix A. Slit Lamp Grading

Meibomian glands (evaluation of the central ten Meibomian gland openings in the mid-portion of the upper eyelid):

- 0 = None (none are plugged).
- 1 = Mild (1 to 2 glands are plugged).
- 2 = Moderate (3 to 4 glands are plugged).
- 3 = Severe (All glands are plugged).
- Lid Erythema
 - 0 = None (normal).
 - 1 = Mild (redness localized to a small region of the lid(s) margin OR skin).
 - 2 = Moderate (redness of most or all lid margin OR skin).
 - 3 = Severe (redness of most or all lid margin AND skin).
 - 4 = Very severe (marked diffuse redness of both lid margin AND skin).
- Lid Oedema
 - 0 = None (normal).
 - 1 = Mild (localized to a small region of the lid).
 - 2 = Moderate (diffuse, most or all lid but not prominent/protruding).
 - 3 = Severe (diffuse, most or all lid AND prominent/protruding).
 - 4 = Very severe (diffuse AND prominent/protruding AND reversion of the lid).

Lashes

- 0 = Normal
- 1 = Abnormal (specify)

Conjunctiva - Erythema

0 = None (normal).

- 1 = Mild (a flush reddish colour predominantly confined to the palpebral or bulbar conjunctiva).
- 2 = Moderate (more prominent red colour of the palpebral or bulbar conjunctiva).
- 3 = Severe (definite redness of palpebral or bulbar conjunctiva).

Conjunctiva - Oedema

- 0 = None (normal).
- 1 = Mild (slight localized swelling).
- 2 = Moderate (moderate/medium localized swelling or mild diffuse swelling).
- 3 = Severe (severe diffuse swelling).
- 4 = Very severe (very prominent/protruding diffuse swelling).

Tear Film Debris

- 0 = None (absence of debris).
- 1 = Mild (presence of debris in inferior tear meniscus).
- 2 = Moderate (presence of debris in inferior tear meniscus and in tear film overlying cornea).
- 3 = Severe (presence of debris in inferior tear meniscus and in tear film overlying cornea. Presence of mucus strands in inferior fornix of on bulbar conjunctiva).
- 4 = Very severe (presence of debris in inferior tear meniscus and in tear film overlying cornea. Presence of numerous AND/OR adherent mucus strands in inferior fornix and on bulbar conjunctiva or filamentary keratitis).

Anterior Chamber Inflammation (Slit beam= 0.3 mm wide, 1.0 mm long)

- 0 = None (no Tyndall effect).
- 1 = Mild (Tyndall effect barely discernible).
- 2 = Moderate (Tyndall beam in the anterior chamber is moderately intense).
- 3 = Severe (Tyndall beam in the anterior chamber is severely intense).

Lens

- 0 = No opacification (normal lens).
- 1 = Mild lens opacification.
- 2 = Moderate lens opacification.
- 3 = Severe lens opacification.

Vitreous

- 0 = No haze (normal lens).
- 1 = Mild vitreous haze.
- 2 = Moderate vitreous haze.
- 3 = Severe vitreous haze.

12.2 Appendix B. Sample SAS Codes for Inferential Analyses

(1) Spearman Correlation Analysis.

For the primary efficacy endpoint:

```
ods output SpearmanCorr = outdata;
proc corr data = indata spearman;
where visitnum = 3 and analysis_eye = "Y";
var CFSchg;
with VMRchg;
run;
```

- In the *outdata* dataset obtained from the above procedure,
 - -n = nCFSchg
 - correlation coefficient = CFSchg
 - p-value = pCFSchg.

For the secondary efficacy endpoint:

```
ods output SpearmanCorr = outdata;
proc corr data = indata spearman;
where visitnum > 0 and analysis_eye = "Y";
var CFSchg;
with VMRchg;
by visitnum;
run;
```

- In the outdata dataset obtained from the above procedure,
 - -n = nCFSchg
 - correlation coefficient = CFSchg
 - p-value = pCFSchg.

(2) Sensitivity Analysis for the primary efficacy endpoint - the MMRM model.

Please only use the observed (i.e., non-imputed) data for this analysis.

```
ods output SolutionF = outdata1;
proc mixed data = indata method = ml;
where visitnum > 0 and analysis_eye = "Y";
class visitnum subjid;
model VMRchg = CFSchg visitnum Base_CFS / noint solution ddfm=KR;
random int / subject = subjid type = UN;
run;
ods output Tests3 = outdata2;
proc mixed data = indata method = ml;
where visitnum > 0 and analysis_eye = "Y";
class visitnum subjid;
model VMRchg = CFSchg visitnum Base_CFS / solution ddfm=KR;
random int / subject = subjid type = UN;
run;
```

- Slope estimate ("Estimate") and standard error ("StdErr") will be obtained from the *outdata1* dataset where EFFECT = "CFSchg".
- P-value ("ProbF") will be obtained from the *outdata2* dataset where EFFECT = "CFSchg".
- Steps for choosing the covariance structure in the RANDOM statements above:
 - 1) Start with TYPE = UN. If the model converges, then stop here and get the results from this model.
 - 2) If the model does not converge, then try to replace UN with TOEPH, ARH(1), TOEP, AR(1), CS, and VC sequentially, and stop when the model converges, or keep going if model does not converge until the convergence criteria are met.
 - 3) Please record which covariance structure is used for which model and put that in the table footnote.
 - 4) Please note that the model covariance structure can be different for different independent variable/dependent variable combinations. But it should be the same for the two procedures used above for the same independent variable/dependent variable combination. Choose the covariance structure that converges for both procedures.

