3 STUDY DESIGN

3.1 General Study Design

The proposed 3-month study is a prospective, open-label, multi-center, phase IV, proof-ofconcept study. The study is designed to assess the effect on the quality of vision of IKERVIS® (1 mg/mL ciclosporin) eye drops administered once daily in dry eye disease (DED) patients with severe keratitis, as well as its safety and efficacy. Thirty-three adult patients are planned to be enrolled in the study in order to obtain 30 completed patients. However, due to the much slower than expected enrollment and budget constraint, this study enrolled 17 patients.

Upon the completion of the Screening Visit, all enrolled study participants will undergo a 2-week wash-out phase during which prior therapies for DED including artificial tears and prohibited ocular treatments must be discontinued. The purpose of the wash-out phase is to eliminate the potential contribution of any prior DED treatment on the efficacy of the study medication. During the wash-out phase patients may use unpreserved artificial tears provided by the Sponsor, up to eight instillations per day in each eye, to relieve their dry eye symptoms. No other topical treatments for DED other than the provided unpreserved artificial tears are allowed during the wash-out phase.

At the Baseline Visit (Day 1) following the 2-week wash-out phase, patients who meet the inclusion criteria for DED and severe keratitis will start the treatment phase with the study treatment (IKERVIS® 1mg/mL). Patients not fulfilling the inclusion criteria or meeting any of the exclusion criteria following the wash-out phase will exit the study without receiving any study medication.

Major inclusion criteria for the eligible eye are DED patients with persistent severe keratitis at the Screening and Baseline Visits defined as the following:

- CFS score of 3, 4 or 5 on the modified Oxford scale, AND
- Visual Maintenance Ratio (VMR) < 0.95, AND
- OSI ≥ 2 , AND
- Variance of $OSI \ge 0.5$.

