During the Baseline Visit, patients will be instructed to instill one drop of study medication (IKERVIS® 1mg/mL) once daily in each eye at bedtime and will be scheduled for three additional study visits, Month 1 (Day 28 ± 3), Month 2 (Day 56 ± 3), and Month 3 (Day 84 ± 7). In addition to the study medication, patients will also be allowed to use unpreserved artificial tears provided by the Sponsor, up to eight instillations per day in each eye, to alleviate their dry eye symptoms. Patients must be instructed not to use artificial tears within 30 minutes before or after use of the study medication and within two hours before a scheduled study visit. All concomitant medications will be recorded on the case report form (eCRF). A change in the use of the study treatments (or any topical eye drops other than the study medication or the Sponsor provided unpreserved artificial tears or topical medications allowed during the study) will be considered a protocol violation. In this phase IV clinical trial, the Month 3 Visit assessments will be used to assess the efficacy (quality of vision and other parameters) and safety of IKERVIS® in DED patients with severe keratitis.

The study flowchart is illustrated in Figure 1.

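### Appendix B fits the sensitivity mixed model by maximum likelihood in 17 patients, so the slope's standard error and p-value come out too small; REML, with the Kenward-Roger option already coded, corrects this

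*SAP*

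**What the plan says.** SAP 8.1.2 lists a mixed model for repeated measures as the first sensitivity analysis of the two primary endpoints. It does not say whether the model is fitted by ML or REML, and Protocol 12.3 does not either. The estimator is set only in SAP Appendix B, part (2), where both procedure calls begin "proc mixed data = indata method = ml".

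The rest of the coded specification is:

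- Fixed effects and small-sample method: "model VMRchg = CFSchg visitnum Base_CFS / noint solution ddfm=KR". The second call is the same apart from dropping the no-intercept option, which only re-parameterises the visit terms.
- Random effect: "random int / subject = subjid type = UN", that is, one random intercept per patient.
- Data: "Please only use the observed (i.e., non-imputed) data for this analysis".
- Reported results: "Slope estimate ('Estimate') and standard error ('StdErr') will be obtained from the *outdata1* dataset" and "P-value ('ProbF') will be obtained from the *outdata2* dataset". All the reported quantities therefore come from ML fits.

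On size, SAP 3.1 records that "due to the much slower than expected enrollment and budget constraint, this study enrolled 17 patients", against 33 planned.

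**The concern.** ML estimates variance components as if the fixed effects were known, so the estimates are biased low. The bias grows as the number of fixed parameters rises relative to the number of patients and records. Here five fixed parameters (three visit means, the CFS-change slope and baseline CFS) are estimated from 17 patients.

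Variances that are too low give a slope standard error that is too small and a p-value that is too small, and Appendix B tells the programmer to report exactly these. The model is meant to check the primary correlation result. With understated uncertainty it would look more supportive of that result than the data allow. Protocol 4.2 says a phase IIIb study will build on this one.

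The usual reason for choosing ML is to compare likelihoods between models with different fixed effects. The SAP makes no such comparison: the covariance structure is picked by which one converges.

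**Working it through.** The documents state no standard error, power or sample-size figure for this model, so there is no plan figure to reproduce first.

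**Inputs from the documents**

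- Patients: 17 enrolled (SAP 3.1).
- Post-baseline visits: 3 (SAP 3.1), so at most 17 × 3 = 51 records.
- Fixed parameters: 3 visit means + 1 slope + 1 baseline CFS = 5 (Appendix B).
- Variance components: 2, random intercept and residual (Appendix B).
- Significance level: 0.05 two-sided (SAP 6).

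**Assumed, because the documents do not give them**

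- Between-patient share of the outcome variance (ICC): 0.3 to 0.7.
- Between-patient share of the variance of CFS change: 0.5 to 0.8.
- Missing visits: 0 to 10%.

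**Step 1: closed-form approximation.** With N independent observations and p fixed parameters, the ML standard error is √((N − p)/N) times the unbiased one.

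- All records: √((51 − 5)/51) = √(46/51) = 0.950.
- Within-patient part (34 df; two visit contrasts and the slope): √(31/34) = 0.955.
- Between-patient part (17 patients; mean, slope and baseline CFS): √(14/17) = 0.907.

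The slope draws on both parts, so a shortfall of about 5% or somewhat more is expected.

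**Step 2: simulation of the coded model.** There were 4,000 trials per scenario with a true slope of zero. Each trial was fitted by ML and by REML, both with the Kenward-Roger adjustment. Under ML the adjustment was computed with the ML and with the REML information matrix, and the ranges cover both. The Monte Carlo standard error of a 5% rate is √(0.05 × 0.95/4000) = 0.34 percentage points.

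| Scenario | Fit | Reported SE / true SD | Actual error of nominal 5% test |
|---|---|---|---|
| 17 patients, 5 fixed parameters | ML + KR | 0.92–0.95 | 6.1–7.4% |
| 17 patients, 5 fixed parameters | REML + KR | 0.98–1.01 | 4.8–5.6% |
| 17 patients, site added | ML + KR | 0.88–0.90 | 7.7–8.4% |
| 17 patients, site added | REML + KR | 0.98–1.00 | 5.2–5.6% |
| 14 patients, 10% visits missing | ML + KR | 0.91–0.92 | 6.9–7.2% |
| 30 patients, 5 fixed parameters | ML + KR | 0.96 | about 6.3% |

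With 17 patients and five fixed parameters, the ML standard error was 5% to 7% below the REML one.

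**Step 3: the source of the bias.** With true variances of 0.50 (intercept) and 0.50 (residual) and complete data, ML averaged about 0.42 and 0.46, and REML averaged 0.50 and 0.50. Kenward-Roger starts from these estimates, so under ML it starts from values that are already too low.

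**Step 4: effect on the p-value.** Take 44 df, about the Kenward-Roger value in the middle scenario. A REML p of 0.050 corresponds to t = 2.015. Dividing by the SE ratio:

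- 2.015/0.95 = 2.121, p = 0.040.
- 2.015/0.93 = 2.167, p = 0.036.

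In the other direction, an ML p of 0.050 corresponds to a REML p of about 0.062 to 0.068.

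**The case against.** **Kenward-Roger is already in the code and exists to correct small-sample standard errors and degrees of freedom.** This is the strongest defence on the numbers, and it fails. The simulated ML results above include the adjustment and are still 5% to 8% short. What stands is that REML alone is not enough either: without Kenward-Roger its standard error was still 3% to 6% short. The two have to be used together.

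**Little depends on this model.** This is true. The primary analysis is Spearman's coefficient, which the choice of estimator does not touch. SAP 6.4 calls the study exploratory, SAP 8 says there is no formal hypothesis testing, and no success rule uses this slope. That limits the seriousness. It does not make the printed standard error and p-value right.

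**It is only sample code.** SAP 1 presents the document as detailed instructions for each analysis, and Appendix B names the exact output fields to report. Nothing in SAP 8.1.2 overrides it.

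**The code does not match the SAP text in other ways, so the figures may not carry over.** This stands as a separate point. SAP 6.3 requires site as a covariate and SAP 8.1.2 an unstructured within-patient error matrix, and the code has neither. The figures above describe the model as coded. Adding site makes the ML shortfall larger; the unstructured error matrix was not simulated.

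**Conclusion.** The concern holds: the estimator is wrong as written, and the error is minor in size. As coded, the slope's standard error is about 5% to 8% too small and a nominal 5% test has an actual error rate of 6.1% to 7.4%. If site is added as SAP 6.3 requires, the shortfall is 10% to 12% and the error rate 7.7% to 8.4%.

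The exact size rests on the assumed correlations and missingness. The direction was the same in every scenario. Seventeen is the number enrolled; fewer patients with post-baseline data would make the bias larger. The calculation reproduced the coded model and its adjustment outside SAS, so small numerical differences from SAS output are possible. The primary correlations and their intervals are not affected.

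**What to change.** In both PROC MIXED calls of Appendix B, part (2), replace METHOD=ML with METHOD=REML and keep DDFM=KR. Use the same setting when the code is adapted for variance of OSI. Add a sentence to SAP 8.1.2 stating that the model is fitted by REML with the Kenward-Roger adjustment.

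The cost is one keyword in two lines of code and one sentence of text. The slope estimate is practically unchanged, and no planned comparison needs ML. The differences between code and text on site and on the error covariance should be settled in the same revision.
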